4.3.3. Safety

The Safety population will include all randomized subjects. All subjects in the Safety population will be analyzed according to the treatment actually received and not according to the treatment they were randomized to receive, in the event there is a discrepancy. Similarly, in any Safety analysis by systemic treatment at study entry (randomization stratification factor), subjects will be analyzed by the actual strata to which they belong and not according to the strata under which they were randomized, in the event there is a discrepancy.

5. Subject Disposition

5.1. Disposition

Subject disposition will be summarized for the ITT population. A disposition of subjects includes the number and percentage of subjects for the following categories: subjects randomized, subjects who completed the study, subjects who discontinued from the study, subjects in the Safety population, subjects in the ITT population, and subjects in the Month 6, Month 12 and Month 36 PP populations. All percentages will be based on the number of subjects randomized.

The reasons for study discontinuation will also be summarized in the disposition table. The reason for study discontinuation includes the following: adverse event, lack of efficacy, lost to follow-up, death, subject voluntarily withdrew, physician decision, sponsor decision, and study cancelled.

Subject disposition data will be presented in a listing.

5.2. Protocol Deviations

The investigator is not to deviate from the requirements from this protocol without prior approval from pSivida Corp. unless necessitated by a medical emergency (i.e., those that impact subject safety or the validity of the study). Any deviation from the protocol, with or without prior pSivida approval, will be recorded including the following information:

- Investigator site
- Subject
- Subject visit
- Description (including associated Significant Protocol Deviation rule number, if applicable)

- Date of occurrence
- Ethics Committee notification date if known
- Significant (Yes/No)

Significant protocol deviations will be defined in the Significant Protocol Deviations Rules document. Each significant deviation will be assigned a rule number. As the study is ongoing, additional significant protocol deviations can also be spontaneously identified or defined during trending and review of protocol deviations by pSivida and/or the project team during the regularly planned study deviation review meetings and the significant Protocol Deviations Rules document will be updated.

All protocol deviations will be reviewed and assessed as to significance prior to each database lock. The list of protocol deviations (significant or minor) that are additionally considered major for the purposes of analysis (i.e. result in exclusion from the PP population) will also be identified prior to each database lock.

6. Demographics and Baseline Characteristics

6.1. Demographics

A summary of demographics and baseline information will be presented for the ITT and Safety populations. Summaries will be generated for the Safety population only if there are randomized subjects who do not receive treatment. The demographic characteristics consist of age (years), sex, race, ethnicity, and iris color. The baseline characteristics consist of baseline height (cm), baseline weight (kg), and baseline body mass index (BMI) (kg/m^2). Body mass index is calculated as $(\text{body weight in kilograms}) / (\text{height in meters})^2$.

A subject's age in years is calculated using the date of the informed consent and date of birth. Age (years), baseline height (cm), baseline weight (kg), and baseline BMI (kg/m^2) will be summarized using descriptive statistics. The number and percentage of subjects by age category (≤ 20 , $20 < 40$, $40 < 60$, ≥ 60), sex (Male, Female), race (White, Black, Asian, American Indian or Alaska Native, Native Hawaiian or Other Pacific Islander, and Other) and ethnicity (Hispanic or Latino, Not Hispanic or Latino), and iris color (Black, Brown, Hazel, Green, Blue, Grey, and Other) will also be reported. Percentages will be based on the total number of subjects in the ITT or Safety population, as applicable.

Subject demographic and baseline characteristics will be presented in a listing.

6.2. Baseline Disease and Ocular Characteristics

A summary of baseline disease characteristics will be presented for the study eye and fellow eye for the ITT and Safety populations. Summaries will be generated for the Safety population only if there are randomized subjects who do not receive treatment. The baseline characteristics consist of study eye, randomization strata for systemic treatment to control uveitis, duration of uveitis (years), number of recurrences in the last 12 months, lens status, presence of cataract, history of vitrectomy procedure and history of incisional surgery to control elevated IOP.

Duration of uveitis is calculated as (Screening date – date of onset of uveitis +1)/ 365.25 and will be summarized using descriptive statistics. For partial onset dates, a missing month will be imputed as January and a missing day will be imputed as the first of the month.

The number and percentage of subjects by study eye (OD, OS), randomization strata (Not receiving systemic treatment, Receiving systemic treatment – corticosteroid therapy, Receiving systemic treatment – immunosuppressive therapy), duration of uveitis (< 2 years, 2 to 5 years, > 5 years), number or recurrences (<= 2, >2), lens status (phakic, aphakic, and pseudophakic), presence of cataract for subjects with a lens status of phakic, history of vitrectomy procedure, and history of incisional surgery to control elevated IOP will also be reported. Percentages will be based on the total number of subjects in the ITT or Safety population, as applicable.

In addition, baseline ocular characteristics will be summarized for the study eye. The baseline ocular characteristics consist of severity of macular edema, IOP (mmHg), and BCVA (letters). Baseline IOP and BCVA will be summarized using descriptive statistics. The number and percentage of subjects by baseline severity of macular edema (CSFT < 300 microns, CSFT >= 300 microns) will also be reported.

Subject baseline disease and ocular characteristics will be presented in a listing.

6.3. Medical History

6.3.1. Non-ocular Medical History

The number and percentage of subjects with any non-ocular medical history and current non-ocular conditions will be summarized overall and for each body system for the ITT population. Body systems will be included as recorded on the eCRF. Percentages will be calculated based on number of subjects in the ITT population.

Subject non-ocular medical history data, including specific details on the condition/diagnosis and start/end dates, will be presented in a listing.

6.3.2. Ocular Medical History

Any clinically significant ocular conditions within the 12 months prior to Screening will be recorded on the eCRF. Subject ocular medical history data, including specific details on the condition/diagnosis, location (OS, OD, and OU), study eye designation, treatment required, and start/end dates, will be presented in a listing.

6.4. Inclusion and Exclusion Criteria

Prior to randomization, the investigator will assess whether the subject fulfills all of the inclusion and exclusion criteria outlined in the protocol. If a subject does not fulfill all of the requirements, the specific inclusion criterion not met or exclusion criterion which was met will be recorded on the eCRF. This information and whether the sponsor granted a waiver will be presented in a listing.

7. Treatments and Medications

7.1. Prior and Concomitant Medications

Medications and systemic/topical treatments for uveitis at study entry will be coded using the WHO Drug Dictionary (WHO201209 version or higher).

All summaries will be provided for ocular medications and non-ocular medications, separately. Ocular medications will be presented by eye (study, fellow).

All medication and systemic/topical treatment data will be presented in listings.

7.1.1 Prior Medications

Prior medications are defined as those medications with a recorded end date prior to the initiation of study treatment. The total number of prior medications and the number and percentages of subjects with at least one prior medication will be summarized by treatment group. The number and percentages of all prior medications will be summarized by treatment group and preferred term. All summaries will be performed using the Safety population.

7.1.2 Concomitant Medications

Concomitant medications are defined as those medications which are taken on or after the initiation of study treatment (Day 1). This includes medications which start prior to Day 1 but continue while the subject is on treatment.

The total number of concomitant medications and the number and percentages of subjects with at least one concomitant medication will be summarized by treatment group. The number and percentages of all concomitant medications will be summarized by treatment group and by ATC level 1 term, ATC level 2 term, and preferred term. An additional summary of the number and percentage of subjects with at least one concomitant medication for each of the specified reasons for medication (recurrence of uveitis, treatment emergent AE, increased IOP, cataract, other) will be summarized by treatment group and by ATC level 1 term, ATC level 2 term, and preferred term. All summaries will be performed using the Safety population.

7.1.2.1 IOP Lowering Medication

The number and percentage of subjects requiring IOP lowering medication to control elevated IOP will be summarized by treatment group, eye (study, fellow), and time interval. Any systemic medications will be summarized as received in both the study and fellow eyes. IOP lowering medications will be identified as those medications with a reason for medication of "Increased IOP". Incidence will be summarized overall (through 6, 12 or 36 months) and for 3 month time intervals through 6 or 12 months and 6 month time intervals from 12 to 36 months.

The number of medications (one, two, \geq three) required to achieve adequate IOP control will also be included in the summary. A single medication must be used for a minimum of 7 days. Multiple medications must be used concurrently for a minimum of 14 days.

A summary of IOP lowering medications will also be presented by geographic region (United States, EMEA, and India) and history of incisional surgery to control elevated IOP (History of

Incisional Surgery, No History of Incisional Surgery). All summaries will be performed using the Safety population.

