9.10.3. IOP Reduction Therapy

Pharmacologic treatment (eyedrops) of elevated IOP must be instituted whenever the IOP is >30 mmHg, and may be instituted at lower IOP levels, at the discretion of investigator 2 and in accordance with the investigator's standard of care. Treatment may include referral to another ophthalmologist. If IOP does not adequately respond to pharmacologic treatment, alternative treatment should be considered (laser, trabeculectomy). The investigator should obtain information on the treatment administered by non-study ophthalmologists for inclusion in the study records.

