11.1.3. Ocular Events

11.1.3.1. Ocular adverse events

The following ocular events will be considered adverse events for the purposes of this trial:

- decrease in visual acuity of at least ≥ 15 letters or ≥ 3 lines from the previous measurement of visual acuity
- moderate or severe (grade 3 or 4) ocular findings compared to the last ophthalmic examination
- worsening of ≥ 2 steps in anterior chamber cell count or vitreous haze, compared to the last ophthalmic examination
- increase in IOP of ≥ 10 mmHg at two visits at least 1 week apart or an increase in IOP to ≥ 25 mmHg

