11.3. Recording of Adverse Events

Changes in a chronic condition or disease, part of the medical history of the patient, that are consistent with natural disease progression are not to be considered as AEs and should not be recorded as such. Medical conditions or diseases present before a subject starts study treatment are only considered AEs if they worsen after the start of the study treatment.

Adverse events can be spontaneously reported or elicited at each study visit through open-ended questioning, examination, or evaluation of a subject. (In order to prevent reporting bias, subjects should not be questioned regarding the specific occurrence of one or more AEs).

The investigator will record all AEs in eCRF. If known, the diagnosis of the underlying illness or disorder should be recorded, rather than its individual symptoms.

The following information should be captured for all AEs: onset and end date, severity, seriousness, relationship to investigational product, action taken and treatment required and outcome. If treatment for the AE was administered, it should be recorded on the appropriate eCRF page.

Completion of supplemental eCRF pages may be requested for AEs and/or laboratory abnormalities that are reported/identified during the course of the study.

The investigator will take or organize all appropriate and necessary therapeutic measures required for resolution of the adverse event. Any medication necessary for the treatment of an adverse event must be recorded on the concomitant medication case report form. If more than one distinct AE occurs, each event should be recorded separately.

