7.2. Ocular Surgeries

All ocular surgeries, including cataract removal, during a subject's participation in the study will be recorded on the eCRF. The number and percentage of subjects with at least one surgery/procedure and at least one surgery/procedure for each of the specified reasons (recurrence of uveitis, treatment emergent AE, increased IOP, cataract, other) will be summarized by treatment group and eye (study, fellow). A frequency distribution for the number of surgeries/procedures during the study per subject will also be presented. All summaries will be performed using the Safety population and percentages will be based on the total number of subjects in the Safety population.

Ocular surgery data, including details on the procedure, eye, study eye designation, start date, and reason for the surgery, will be presented in a listing.

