7.2.1 Surgical Intervention to Control Elevated IOP

The number and percentage of subjects requiring any surgical intervention to control elevated IOP will be summarized by treatment group, eye (study, fellow), and time interval. Ocular surgeries with a reason of "Increased IOP" will be included in the summary. Incidence will be summarized overall through 6 months and for 6 month time intervals through 12 (or 36) months.

A summary of incidence of surgical interventions to control elevated IOP will also be presented by geographic region (United States, EMEA, and India) and history of incisional surgery to control elevated IOP (History of Incisional Surgery, No History of Incisional Surgery). All summaries will be performed using the Safety population.

A listing of all subjects requiring surgical interventions to control elevated IOP will be provided. This listing will include details relating to the IOP-lowering surgical intervention (procedure, eye, study eye designation, and date procedure performed), demographic and baseline ocular

characteristics including BCVA and IOP, the last available BCVA and IOP values as of the data cut-off, and the date of first recurrence of uveitis, if any.

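### IOP-lowering drugs, IOP surgery and cataract surgery are picked out only by a recorded reason that overlaps with an adverse-event category, so their counts may be understated

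*SAP*

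**What the plan says.** Three treatment-based outcomes are each defined by the reason entered with the record:

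- **IOP-lowering drugs (SAP 7.1.2.1):** "IOP lowering medications will be identified as those medications with a reason for medication of" increased IOP.
- **IOP surgery (SAP 7.2.1):** "Ocular surgeries with a reason of" increased IOP are included.
- **Cataract surgery (SAP 7.2.2):** the same construction with the reason cataract, restricted to eyes phakic at entry.

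None of the three sections adds a rule by drug class, preferred term or procedure name.

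The reasons on offer for drugs (SAP 7.1.2) are the "specified reasons for medication (recurrence of uveitis, treatment emergent AE, increased IOP, cataract, other". The list for surgery (SAP 7.2) is the same: "specified reasons (recurrence of uveitis, treatment emergent AE, increased IOP, cataract, other".

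Protocol 11.1.3.1 counts as an ocular adverse event an "increase in IOP of ≥ 10 mmHg at two visits at least 1 week apart or an increase in IOP to ≥ 25 mmHg". Protocol 9.10.3 says that drug treatment "must be instituted whenever the IOP is >30 mmHg" and allows it at lower pressures at the investigator's discretion. Protocol 11.3 adds: "Any medication necessary for the treatment of an adverse event must be recorded on the concomitant medication case report form".

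SAP 3.2 lists both IOP treatment and cataract procedures among the safety endpoints.

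**The concern.** The list mixes a generic category (*treatment emergent AE*) with specific ones (*increased IOP*, *cataract*) that are often instances of it. A site that logs a glaucoma drop or a cataract extraction under the generic category has followed the protocol, yet the record leaves the table built for that outcome.

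Three things depend on the selection:

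- **Incidence tables.** 7.1.2.1 reports IOP drugs by eye, time interval, number of drugs, region and history of incisional surgery. 7.2.1 does much the same for IOP surgery, and 7.2.2 reports cataract surgery by eye and interval.
- **Subgroups.** SAP 8.1.4 (efficacy) and 9.2.1 (BCVA) split subjects by IOP-treatment status. A missed record can put a treated eye in the untreated group.
- **Complication windows.** SAP 9.1.8 counts complications from first use of an IOP-lowering drug, or from the surgery. If the first record is missed, the window starts late or not at all.

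Absolute incidence matters here because Protocol 5.4 argues for a better IOP profile than Retisert partly on cross-trial rates of IOP-lowering surgery (4.8% versus 33.8% in DME).

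**Working it through.** **1. The plan's own figure.** The documents give no expected rate or coding-error rate for these outcomes. The only design figure is 89% power for the primary endpoint (SAP 4.1: 40 sham, 80 FAI, recurrence-free rates 0.600 and 0.880). With the continuity-corrected formula it reproduces at 89.2%. This point does not affect it.

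**2. Do the categories really overlap?** Take a study eye whose IOP exceeds 30 mmHg after Day 1.

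- Entry excludes a study-eye IOP above 21 mmHg (Protocol 8.2), so the reading is "an increase in IOP to ≥ 25 mmHg" and hence an adverse event.
- Its onset is after injection, so it is treatment-emergent under SAP 9.1.
- Drug treatment is mandatory under Protocol 9.10.3.
- The drug goes on the concomitant medication form, where its reason is recorded.

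Both *increased IOP* and *treatment emergent AE* are then true. For treatment started at lower pressures the overlap is possible but not certain, because the reading may miss both limbs of the adverse event rule. For cataract, 11.1.3.1 gives no specific criterion. A new or worsened cataract fits the general definition in Protocol 11.1.1.

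**3. What settles the choice?** Nothing in the documents says whether one or several reasons may be recorded, which takes precedence, or whether reason and coded term are reconciled before lock.

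**4. Size, as a range.** Let m be the share of treated subjects whose every qualifying record carries another reason, taken as equal in both arms.

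Reported rate = true rate × (1 − m). Reported difference = true difference × (1 − m). The ratio between arms is unchanged.

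The documents do not give m, so it is varied. The true rates are assumptions borrowed from the low-dose Iluvien DME trials: Protocol Table 2 for IOP at 36 months, Protocol 5.3.2.2.2 for cataract surgery in phakic eyes. No IOP-drug rate is given, so IOP of 30 mmHg or more stands in for it.

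| Outcome (active / sham) | m = 0 | m = 10% | m = 25% | m = 50% |
|---|---|---|---|---|
| IOP drug, proxy: rates | 18.4 / 4.3% | 16.6 / 3.9% | 13.8 / 3.2% | 9.2 / 2.2% |
| difference (points) | 14.1 | 12.7 | 10.6 | 7.1 |
| IOP surgery: rates | 4.8 / 0.5% | 4.3 / 0.45% | 3.6 / 0.38% | 2.4 / 0.25% |
| difference (points) | 4.3 | 3.9 | 3.2 | 2.2 |
| Cataract surgery: rates | 75 / 23% | 67.5 / 20.7% | 56.3 / 17.3% | 37.5 / 11.5% |
| difference (points) | 52 | 46.8 | 39 | 26 |

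Example: cataract surgery at m = 10% gives 75 × 0.9 = 67.5 and 23 × 0.9 = 20.7, a difference of 46.8. The ratios stay at 18.4/4.3 = 4.28, 4.8/0.5 = 9.6 and 75/23 = 3.26.

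Small counts make single records matter. IOP surgery at 4.8% of 80 FAI subjects is 0.048 × 80 = 3.8, about four people. One of them recorded only under another reason lowers the rate by 1/80 = 1.25 points, about a quarter of 4.8.

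m is a share of subjects. A subject with several records is lost only if all of them are coded elsewhere, so a record-level miscoding rate overstates m.

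**The case against.** **The list may work as intended.** With dedicated entries for IOP and cataract, *treatment emergent AE* can be read as the residual category for other events. The case report form and its completion guide are not in the documents, and they may require the specific reason or allow several. This stands, and it means the documents show a risk only. A reader might infer that these outcomes *are* undercounted. That does not follow.

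**Other safety outputs do not use the reason.** Elevated-IOP and cataract adverse events are selected by preferred-term list (SAP 9.1.8). Measured IOP is tabulated against fixed thresholds (9.2.2), and lens and cataract changes are tabulated by eye (9.2.4). This also stands. A reader might conclude that the main safety outcomes as a whole are compromised, but only the treatment-based ones are.

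**Misplaced records would be visible.** All concomitant drugs are tabulated by ATC level and preferred term, both overall and within each reason (7.1.2), and ocular drugs are shown by eye (7.1). Any ocular surgery is summarised, and the listing shows procedure and reason (7.2). A careful reader could find the discordant records. These outputs do not, however, correct the three endpoint tables, the subgroup flags or the complication windows.

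**No bias between arms is shown.** Investigators are masked after Day 1, and nothing suggests that coding would differ by arm. With equal m the FAI/sham ratio does not move. A reader might infer that the rule flatters the insert against sham. The documents support only possible shrinkage of incidence and absolute difference.

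**The endpoint is about purpose, and the reason field records purpose.** Protocol 5.3.2.2.2 mentions vitrectomy done for elevated IOP or for device removal, so a procedure term alone can mislead. This stands and shapes the fix: coded terms should be added to the reason, not put in its place.

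**Conclusion.** The concern holds as a risk in the definition. The reason categories overlap, and for a mandated treatment of a study-eye IOP above 30 mmHg after Day 1 the overlap is built into the protocol. No precedence rule, coded-term check or reconciliation is stated. Reported incidence of IOP drug use, IOP surgery and cataract surgery may be understated, and the IOP-treatment subgroups and complication start dates may be misclassified.

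The size cannot be derived from the documents. Under equal miscoding, incidence and absolute difference fall by the factor 1 − m. The loss is zero if several reasons can be recorded or sites always choose the specific one. The rates in the table are borrowed from DME trials and serve only as illustration. Measured IOP, the preferred-term adverse event summaries, the primary analysis and the sample size are unaffected. This is a cheap improvement worth making. It is not evidence that the safety results are wrong.

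**What to change.** In SAP 7.1.2.1, 7.2.1 and 7.2.2, define each outcome as a record with the specific reason **or** a matching coded term:

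- **IOP drugs:** WHO Drug class for antiglaucoma preparations and systemic carbonic anhydrase inhibitors.
- **IOP and cataract surgery:** a pre-specified list of procedure terms, keeping the phakic-at-entry restriction for cataract.

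Before each lock, list the records where reason and term disagree and have them adjudicated for purpose. The Clinical and Data Management staff are suited to this, because SAP 4.2.1 keeps them masked to subject-level treatment until after the Month 36 lock. State whether several reasons may be recorded and, if not, which takes precedence. Apply the resulting status to 8.1.4, 9.1.8 and 9.2.1, and record the change in SAP section 11.

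The cost is SAP wording and a short term review; drugs and procedures are already recorded and drugs already coded. Some drugs or procedures given for another purpose will enter the review and have to be ruled out. If the change is made after the Month 6 lock, when the sponsor and the biostatistics team are unmasked, it must be documented as a post-unmasking change in section 11.2.
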